Quebec score and gait speed will be used to test our specific hypotheses about short-term (immediately post-treatment) and longer-term (6-months post-randomization) changes in disability and pain severity. We will use linear mixed models with time (baseline, 8 weeks and 6 months) and the group*time interaction as fixed effects while controlling for repeated measures using an unstructured correlation matrix between time points. The effect of time will be treated as categorical. No main effect for treatment is included as the baseline means are assumed and constrained to be equal due to randomization. We will also control for site and sex as fixed effects since these are stratification factors in the randomization. We will use linear contrasts to test HIP+ versus SFR at 8 weeks and 6 months (Aim 1). GLMM assumptions include homoscedasticity, normality, and linearity using standard graphical methods, the Shapiro-Wilk test, and Box-Cox test respectively. If model assumptions are violated, we will consider transformations (e.g. Box-Cox method) that can be applied but maintain interpretability. We will test the secondary outcome measures related to Aim 1 in the same fashion to identify which outcomes should be considered in future trials.

The rates of individual adverse events and serious adverse events that occur >10% and adverse events classified by organ system and relatedness will be calculated for each group and compared using Chi-square or Fisher's exact tests.

Aim 2: Hypothesis. Reductions in hip joint pain, increases in hip strength and increases in functional self-efficacy will be associated with improvements in LBP-related disability and physical function.

Two sets of regression analyses will be used to determine the degree to which changes in hip pain, hip strength and functional self-efficacy explain changes in LBP-related disability and physical

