function, as measured by change in Quebec score and gait speed, respectively. The first set of models will examine the change from baseline to immediately post-treatment (8 weeks) and the second set from immediately post-treatment to 6 month follow up for Quebec scores. The second set will do the same but for changes in gait speed. Sequential Multiple Linear Regression Models will be used to test if predictors of interest are related to the outcomes after adjusting for potential covariates. This can be evaluated by testing the ΔR^2 that results from adding subsequent blocks of predictors to each model. If the block is significant, then the tests of the individual predictors will be examined. In the first block will be covariates that are potential confounders (i.e. age and sex) as well as the baseline values of hip pain, hip strength and self-efficacy. [Internal rotation strength relative to body mass, will be chosen as a representative hip strength measure, based on strength of association in our original data]. In the second block of each model will be the treatment group and change values for the predictors of hip pain, hip strength and self-efficacy. All assumptions for models will be tested: multicollinearity by examining the Variance Inflation Factor and Condition Index; normality using Shapiro-Wilk test; Homoscedasticity using the Breusch-Pagan test; and Linearity using the Box-Cox test. If assumptions are violated, transformations suggested by a Box-Cox test will be employed; if that fails Generalized Linear Models will be used.

Additionally, as an exploratory analysis a path analysis will be used to test if the relationship between baseline hip measures (pain, strength, and self-efficacy) and changes in disability and function are mediated by changes in the hip measures. Model fit will be examined using the chi-square model fit test, and standard fit indices (Root Mean Square Error of Approximation (RMSEA), Standardized Root Mean Residual (SRMR), Comparative Fit Index (CFI), and the Tucker-Lewis Index (TLI)) and to address the research question the significance of the indirect effect will be examined. It is likely that this analysis will be underpowered given the number of variables included. However, the analysis will provide a basis for further hypothesis generation and inform the follow-up study.

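### Aim 2 checks linearity with the Box-Cox test, which examines the outcome scale and has little power against curvature in the hip-change predictors

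*Combined protocol and SAP*

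**What the plan says.** Section 10 (DATA), Statistical Analysis, Aim 2, plans sequential linear regressions. The outcomes are changes in "function, as measured by change in Quebec score and gait speed, respectively". The first block holds "covariates that are potential confounders (i.e. age and sex) as well as the baseline values of hip pain, hip strength and self-efficacy". The second is described as follows: "In the second block of each model will be the treatment group and change values for the predictors of hip pain, hip strength and self-efficacy".

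Each model assumption is paired with a named diagnostic. Multicollinearity goes to the Variance Inflation Factor and Condition Index, and the list continues with "normality using Shapiro-Wilk test", the Breusch-Pagan test for homoscedasticity, and then "Linearity using the Box-Cox test. If assumptions are violated, transformations suggested by a Box-Cox test will be employed". That one remedy covers every failure, with generalized linear models as the fallback. For Aim 2 the section names no residual plot, polynomial term or spline term in any predictor.

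The Aim 1 paragraph of the same section makes a similar pairing for the mixed models: "linearity using standard graphical methods, the Shapiro-Wilk test, and Box-Cox test respectively". Read in order, that assigns the Box-Cox test to linearity there too.

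**The concern.** Linearity in Aim 2 means that the expected change in Quebec score or gait speed is a straight-line function of each hip-change predictor. The Box-Cox test takes those straight lines as given. It asks whether a power of the outcome would bring the errors closer to normal with constant variance. A bend in one predictor therefore need not move its result, while skewed errors around genuinely straight lines will.

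Aim 2 is one of the trial's two specific aims, and its purpose is to say how far hip changes account for changes in disability and function. If the only linearity check cannot see a plateau or turning point, the report may state that linearity was checked and give one averaged slope for a relation that is not straight. The stated remedy also acts on the outcome, which is the wrong place to correct curvature in a single predictor.

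**Working it through.** **No stated figure to reproduce.** The documents give no power, error rate, residual SD or effect size for Aim 2. The check is therefore structural, with simulation under stated assumptions.

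**Inputs from the documents.** 180 participants randomised 1:1 (section 6); two-sided 5% tests (section 10); first block of 5 terms (age, sex, three baseline hip measures); second block of 4 terms (group, three change scores). Residual degrees of freedom: 180 - 1 - 9 = 170.

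**What the test contains.** For a positive outcome y, Box-Cox sets y(λ) = (y^λ - 1)/λ and regresses it on the fixed predictor matrix X. The profile log-likelihood is ℓ(λ) = -(n/2) log[RSS(λ)/n] + (λ - 1) Σ log y. The test statistic is 2[ℓ(λ̂) - ℓ(1)], referred to chi-square on 1 df. X is the same under both hypotheses, so no alternative adds a curved term in a predictor. Change scores can be negative, so the outcome was shifted to be positive; different shifts gave similar results.

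**Assumptions.** Residual SD 12 Quebec points; linear effects of 3 points per SD, except where one predictor has the shape shown. The comparator is a 3-df F test adding one non-linear term for each of the three change predictors. Ranges cover repeat runs of 500 to 2,000 datasets per setting.

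| True shape in one change predictor (normal errors) | Box-Cox rejects | Direct test rejects |
|---|---|---|
| Linear | 4-5% | 3-7% |
| Plateau: slope 6 below the mean, 0 above | 4-5% | 31-34% |
| Plateau: slope 9 below the mean, 0 above | 4-5% | 62-67% |
| Turning point, slope 6 or 9 | 4-6% | 86-100% |
| Quadratic, 3 points per SD squared | 10% | 95-96% |

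A second set-up with error SD 1 gave the same pattern. Quadratic terms of 0.2, 0.3 and 0.4 were found in 7%, 16% and 31% by Box-Cox, against 84%, 99% and 100% by squared terms. The 3-point quadratic above is 3/12 = 0.25 on that scale, and its 10% lies between 7% and 16%, as it should. With an assumed 15% loss (0.85 × 180 = 153), the 0.3 quadratic was found in 14% against 97%.

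**What a straight line reports.** For a standardised symmetric predictor x, the fitted slope is E[x f(x)].
- Plateau with slope 6 below the mean: 6 × 0.5 + 0 × 0.5 = 3, which is half the true slope below the mean and a false slope above it. Simulation gave 2.9.
- Turning point with slopes +6 and -6: 6 × 0.5 - 6 × 0.5 = 0.

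**Linear models with skewed errors.**

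| Residual skewness | Box-Cox rejects | Shapiro-Wilk rejects | Rejected by Box-Cox but not by the other listed tests |
|---|---|---|---|
| 0.5 | 63-70% | 55-62% | 14-16% |
| 1.0 | 98% to over 99% | 99% | 0.3-1% |

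The direct test stayed at 3-7% in these settings.

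**Aim 1.** Time is treated as categorical, and the other listed fixed effects (group-by-time, site, sex) are categorical too. There is no continuous predictor whose linearity could fail.

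**The case against.** Four arguments on the other side deserve weight.

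- **False alarms.** A reader might infer that the Box-Cox check is what would push skewed but linear models into transformation. The plan's own rule does not support that. Any failed assumption triggers the same remedy, and Shapiro-Wilk fails nearly as often. Box-Cox alone adds 14-16% at skewness 0.5 and 1% or less at skewness 1.0. This objection stands.

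- **Effect on conclusions.** A reader might also infer that both kinds of error change the Aim 2 conclusion. That is not shown. The Aim 2 hypothesis is one of association, judged by the block test and then by individual predictors. With skewed errors, the block decision on the raw and transformed outcome agreed in 99.3-99.6% of datasets, and the decision for one change predictor in 94-98%. With the 6-point plateau, the linear model still detected the block in 99% and that predictor in 82%. The turning point is the exception, because its fitted slope is near 0.

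- **Power is low, not zero.** When the whole predictor index is curved and R-squared is about 0.75, Box-Cox detects it in 77-100%. At R-squared of about 0.45 this falls to 7-22%. Nothing in the documents says that a plateau or turning point is expected.

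- **Other provisions.** Outlier screening and the generalized linear model fallback were not simulated. Neither is described as a check of predictor shape, and the fallback applies only after a failure has been noticed.

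The authors may have intended Box-Tidwell, which does act on predictors. The text does not say so, and the remedy it names is a Box-Cox transformation.

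**Conclusion.** The Aim 2 linearity check is wrong as written, with modest severity. It tests the outcome scale, and no other listed Aim 2 check targets curvature in the change predictors. In the assumed SD-12 setting its detection rate for curvature in one predictor is about 5-10%, close to its 5% false-positive rate, while a direct test reaches about 31-96%. The percentages rest on assumed effect sizes, SD and curve shapes. The mechanism does not, because the test has no predictor-curvature term.

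The consequence is a possible misdescription of how hip changes relate to outcome and, with a turning point, a relation that could be hidden. A reader might take the matching Aim 1 wording to mean that the primary treatment comparison is compromised. The documents do not support that: all listed fixed effects there are categorical, and Aim 1 only commits to considering transformations that keep results interpretable. In Aim 1 this is a labelling error.

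**What to change.** In section 10, Aim 2, replace the Box-Cox linearity check with a prespecified joint test of one non-linear term (quadratic or 3-knot restricted cubic spline, chosen in advance) for each of the three change predictors, together with component-plus-residual plots. Apply it to each Aim 2 model. The plots matter because the joint test itself finds the 6-point plateau in only about a third of trials.

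Keep the linear model and its block test as the planned analysis, so that the diagnostic does not select the model. If the joint test rejects, also report the non-linear fit on the original outcome scale. State that outcome transformation is not the remedy for non-linearity in a predictor.

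In Aim 1, delete the Box-Cox linearity label as a minor correction.

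The cost is a few sentences of wording, 3 degrees of freedom in the check (170 - 3 = 167 remain with all 180 participants analysed) and slightly longer reporting. No new data are needed. The change does not close the Shapiro-Wilk route to transforming a skewed but linear model, and it is not meant to.

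### Aim 2 relies on Box-Cox for change scores that will include zero and negative values, where it is undefined as written, and the fallback model is unspecified

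*Combined protocol and SAP*

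**What the plan says.** The text is in the combined protocol and SAP, Section 10 (Data), Statistical Analysis.

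- **Outcomes.** Aim 2 explains changes in LBP-related disability and physical "function, as measured by change in Quebec score and gait speed, respectively". The Quebec models cover two intervals, baseline to 8 weeks and 8 weeks to 6 months. For gait speed, "The second set will do the same but for changes in gait speed". That makes at least four models.
- **Predictors.** "In the second block of each model will be the treatment group and change values for the predictors of hip pain, hip strength and self-efficacy". Three of the second-block terms are therefore change scores too.
- **Diagnostics.** All assumptions are to be tested in these models: normality by Shapiro-Wilk, homoscedasticity by Breusch-Pagan, and "Linearity using the Box-Cox test".
- **Remedy.** "If assumptions are violated, transformations suggested by a Box-Cox test will be employed; if that fails Generalized Linear Models will be used". No shift constant, signed-data transformation, GLM family or link is named.
- **Aim 1, for contrast.** The mixed models use scores at each visit, and the wording is permissive: "If model assumptions are violated, we will consider transformations (e.g. Box-Cox method) that can be applied but maintain interpretability".

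**The concern.** The one-parameter Box-Cox family raises the outcome to an estimated power, or takes its log. It exists only for outcomes above zero. A change score is a signed quantity, and some participants will not change or will move the other way. The method named as linearity check and as first remedy is therefore undefined on the Aim 2 outcomes as coded.

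The two uses differ in force. The remedy is conditional on a failed assumption, but once triggered it is mandatory. The linearity check is planned for every Aim 2 model.

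Two further problems would remain even for positive outcomes. Box-Cox looks for a power of the outcome, so it does not test whether each predictor acts linearly. A monotone transformation of the outcome also cannot remove unequal variance that follows a predictor rather than the outcome's level.

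At stake are the interpretability and pre-specification of one of the trial's two specific aims. The analyst would choose the shift, or the family and link, after seeing the data. Coefficients might then no longer be in Quebec points or m/s.

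**Working it through.** The plan gives no figure to reproduce on this point. The documents state 180 participants (Section 6, Design and Randomization Plan) and a pilot gait-speed gain of +0.07 m/s with the hip intervention (Section 6, Interventions). They give no SD for either outcome and no mean Quebec change, so those are assumed below.

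**1. Share of non-positive change scores.** Under a normal model, P(change ≤ 0) = Φ(−mean/SD).

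| Outcome, interval | Mean | SD | P(≤ 0) | Expected of 180 |
|---|---|---|---|---|
| Quebec improvement, 8 weeks | 12 | 12 | Φ(−1.00) = 16% | 29 |
| | 12 | 15 | Φ(−0.80) = 21% | 38 |
| | 5 | 12 | Φ(−0.42) = 34% | 61 |
| | 5 | 15 | Φ(−0.33) = 37% | 66 |
| Gait speed, 8 weeks | 0.07 | 0.10 | Φ(−0.70) = 24% | 44 |
| | 0.07 | 0.15 | Φ(−0.47) = 32% | 58 |
| | 0.07 | 0.20 | Φ(−0.35) = 36% | 65 |
| Either, 8 weeks to 6 months | 0 | any | Φ(0) = 50% | 90 |

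If Quebec change is coded follow-up minus baseline, improvement is negative and the non-positive share becomes 63% to 84%. Non-positive values are practically certain. In the most favourable gait-speed row, the chance that all 180 changes are positive is (1 − 0.242)^180, about 2 × 10⁻²².

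**2. The remedy as written.** A simulated right-skewed change score was used (gamma with shape 2 and scale 0.1, minus 0.13; n = 180; 34% at or below zero).

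- One-parameter Box-Cox stops because the data must be positive.
- Gamma and inverse-Gaussian GLMs with log link fail on the same data. A Gaussian GLM runs, but with identity link it is the original regression.

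**3. What could be run instead.** On the same data, Yeo-Johnson works (λ = −3.19; Shapiro-Wilk p = 0.36). Box-Cox after a shift also works, but the power depends on where the minimum is placed:

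| Minimum moved to | 0.001 | 0.01 | 0.1 | 0.5 | 1.0 |
|---|---|---|---|---|---|
| λ | 0.34 | 0.24 | −0.22 | −1.79 | −3.63 |

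**4. Does the shift change the block test?** Rarely. In one set of simulations (n = 180, error skewness 0.5 or 1, five shifts), all shifts gave the same 5% decision on ΔR² in at least 99.7% of 300 runs per scenario. In another (500 runs, skewed errors, 29% non-positive), the shift changed the decision in 1.2%.

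**5. How often would the remedy be triggered?** At n = 180, simulated Shapiro-Wilk rejection was 29% for skewness 0.3, 34% for t with 10 df, 66% for skewness 0.5 and 78% for t with 5 df. Mild departures usually pass; moderate ones often do not.

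**6. Does Box-Cox do the other jobs?** Simulations with n = 160 and assumed effect shapes, nominal level 5%:

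- Variance depending on a predictor: null rejection was about 19% with ordinary least squares, about 19% after shifted Box-Cox, and 7.5% with HC3.
- Quadratic effect of a predictor: Box-Cox flagged a problem in about 20% of runs, a direct curvature term in 100%.

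The sizes in step 6 depend on the assumed strength of the heteroscedasticity and curvature. The direction follows from what Box-Cox estimates.

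**The case against.** The strongest reply is that this is under-specification in a contingent clause of an explanatory analysis. The transformation applies only if assumptions fail. A competent analyst would add a shift or use Yeo-Johnson, and the block test would hardly move. Transformation can even help: with error skewness 1, the simulated power of the block test was 91% transformed against 81% on the original scale. Naming the shift, family and link would close the gap with less rewriting.

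Much of this stands, and it limits the point. It does not answer three things: the linearity check is unconditional and undefined on these outcomes, it would not detect curvature in a predictor reliably even after a shift, and the remedy leaves predictor-dependent variance uncorrected.

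A reader might also infer more than the documents support:

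- **That the remedy cannot be run at all.** Step 3 shows that a shifted or signed-data version can be run; the plan names neither.
- **That participants who did not improve would be dropped.** Nothing in the plan says so. In the check the procedure stopped rather than deleting anyone. With follow-up minus baseline coding, the negative Quebec values belong to those who improved.
- **That Aim 1 needs the same change.** Aim 1 models visit scores, not signed changes. Its wording is discretionary and already asks that transformations be applicable and interpretable.

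**Conclusion.** The point holds for Aim 2. The Box-Cox procedure is undefined on the planned outcomes as written, is the wrong tool for checking linearity in the predictors or correcting predictor-dependent variance, and is backed by a GLM step with no family or link. Under the assumed means and SDs, about 16% to 37% of 8-week Quebec improvements are at or below zero, and about half of the later changes if their mean is near zero. The exact shares rest on those assumptions; the presence of non-positive values does not depend on any plausible choice among them.

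The consequence is moderate: choices made after seeing the data and coefficients in units that are hard to read. The choice of shift alone probably has little effect on the ΔR² test. The Aim 1 treatment comparison is not affected.

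**What to change.** Replace the Aim 2 linearity check and remedy with the following:

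- Outcomes stay in Quebec points and m/s.
- Linearity is checked with partial-residual plots or an added spline or quadratic term for each continuous predictor.
- If residual diagnostics are poor, coefficients and the block test use HC3 standard errors or bootstrap intervals, with one of the two named in advance.
- Any transformed analysis is a sensitivity analysis only, with a pre-specified signed-data transformation or shift. If a GLM is kept, its family and link are stated.

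Leave the Aim 1 text as it is.

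The cost is a few sentences in the plan and standard software options. Intervals may be slightly wider, and some power is lost if errors are markedly skewed (81% against 91% in the simulated case above). HC3 reduced the excess error in the check but did not remove it entirely (7.5% against a nominal 5%).

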11. CONFIDENTIALITY

Will participants be audiotaped, photographed or videotaped during this study? In some cases for publications, presentations, and/or education purposes, but only with expressed written consent (separate section included on informed consent document). Those participants who willingly identify themselves via the informed consent will be considered for use of their likeness for these purposes.

How will subject identity be protected?

The risk of breaching subject confidentiality will be minimized by identifying all participants by code numbers and by securing all data in locked files accessible only to research personnel. Neither the participant's name or nor any identifying information will be used in any publication or presentation resulting from this study.

Is there a Certificate of Confidentiality in place for this project? (If so, please provide a copy).
No

12. CONFLICT OF INTEREST

(For information on disclosure reporting see: <http://www.udel.edu/research/preparing/conflict.html>)

Do you have a current conflict of interest disclosure form on file through UD Web forms? Yes

Does this project involve a potential conflict of interest*? No

* As defined in the [University of Delaware's Policies and Procedures](#), a potential conflict of interest (COI) occurs when there is a divergence between an individual's private interests and his or her professional obligations, such that an independent observer might reasonably question whether the individual's professional judgment, commitment, actions, or decisions could be influenced by considerations of personal gain, financial or otherwise.

If yes, please describe the nature of the interest: Not applicable

13. CONSENT and ASSENT

Consent forms will be used and are attached for review (see Consent Template under Forms and Templates in IRBNet)

Additionally, child assent forms will be used and are attached.

Waiver of Documentation of Consent (attach a consent script/information sheet with the signature block removed).

Waiver of Consent (Justify request for waiver)

14. Other IRB Approval

Has this protocol been submitted to any other IRBs? Yes

If so, please list along with protocol title, number, and expiration date.

Duke University: Manual Therapy and Strengthening for the Hip in Older Adults with Chronic Low Back Pain: A Randomized Clinical Trial; Pro00100410; expiration date: 8/29/2019

University of Pittsburgh

1. Evaluating the Effects of Two Different Physical Therapy Interventions for Low Back Pain in Older Adults: A Multi-Site Clinical Trial; MOD19050337-001; expiration date: 6/18/2020

2. Evaluating the Effects of Two Different Physical Therapy Interventions for Low Back Pain in Older Adults: A Multi-Site Clinical Trial Data Coordinating Center; PRO18050723; expiration date: 9/16/2019

15. Supporting Documentation

Please list all additional documents uploaded to IRBNet in support of this application.

Informed Consent Form

Mailing Packet Site-Specific Documents:

- Cover Letter for Initial/8 week follow-up/16 week follow-up mailing packets
- Directions to Clinical Site (e.g. STAR Campus)

Data Collection Forms

UD Recruitment Materials

- Verbal Recruitment Script
- Print Advertisement
- Flier with Pull Tabs
- Text for Newsletters

New UD Recruitment Materials

Website Materials

UD CITI Training Certificates

